8.3.3 Follow-up of AEs and SAEs

After the initial AE/SAE report, the investigator is required to proactively follow each trial subject at subsequent visits/contacts. All AEs/SAEs will be followed until resolution, stabilization, the event is otherwise explained, or the trial subject is lost to follow-up (as defined in Section 7.3). Further information on follow-up procedures is provided in Section 10.3.1.7.

BioNTech SE
Confidential

Clinical Trial Protocol BNT162-14 Page 51 of 91 Version: 4.0 Date: 20 JAN 2022

The investigator is obligated to perform or arrange for the conduct of supplemental measurements and/or evaluations as medically indicated or as requested by the sponsor to elucidate the nature and/or causality of the AE or SAE as fully as possible. This may include additional laboratory tests or investigations, histopathological examinations, or consultation with other healthcare professionals.

New or updated information will be recorded in the originally completed CRF.

The investigator must submit any updated SAE data to the sponsor within 24 h of receipt of the information as indicated in Section 10.3.1.10.

All ongoing AEs/SAEs will be followed until resolution, considered by the investigator to be stable or chronic (resolved with sequelae), the trial subject is lost to follow-up or the trial subject withdraws consent. If no final status is reached by the time the trial subject is discharged from the trial, the investigator must confirm the unavailability of a final status.

8.3.4 Regulatory reporting requirements for SAEs

Prompt notification of an SAE by the investigator to the sponsor is essential so that legal obligations and ethical responsibilities for the safety of trial subjects and the safety of a trial treatment under clinical investigation are met.

The sponsor has a legal responsibility to notify both the local regulatory authority and other regulatory agencies about the safety of a trial treatment under clinical investigation. The sponsor will comply with country-specific regulatory requirements relating to safety reporting to the regulatory authority, IECs, and investigators. The execution of expedited reporting to the different entities may be delegated as detailed in the trial Safety Management Plan.

Safety reports will be prepared for suspected unexpected serious adverse reactions (SUSARs) according to local regulatory requirements and sponsor policy and forwarded to investigators as necessary.

For the IMP, it is the sponsor's or delegate's responsibility to perform SUSAR reporting to the regulatory authority, the IEC, and the other investigators as required by national law and applicable guidelines.

An investigator who receives an investigator safety report describing an SAE or other specific safety information (e.g., summary or listing of SAEs) from the sponsor should review it and then file it together with the IB. If required by local requirements, the investigator will notify the relevant IEC.

8.3.5 Pregnancy

For WOCBP, pregnancy tests will be performed using commercial kits at the times given in the SoA (see Section 1.3).

Pregnancy information (information on trials subjects who become pregnant or information for female partners of male trial subjects who become pregnant) will be collected for pregnancies that occurred after the date of the first injection of IMP until the subject terminates or completes the study.

BioNTech SE
Confidential

Clinical Trial Protocol BNT162-14 Page 52 of 91 Version: 4.0 Date: 20 JAN 2022

Pregnancy information will only be collected after obtaining written informed consent from the pregnant female subject (or if a male subjects' partner becomes pregnant, written informed consent from both).

If a pregnancy is reported, the investigator should inform the sponsor within 24 h of learning of the pregnancy and should follow the procedures outlined in Section 10.4.

Abnormal pregnancy outcomes (e.g., spontaneous abortion, fetal death, stillbirth, congenital anomalies, ectopic pregnancy) are considered SAEs.

8.3.6 Death events

Any death that occurs within the observation period will be reported as an SAE.

In case of a fatal event, the event term should not be "death" but the underlying event which led to death (death = outcome). If there is more than one AE in a fatal case, only for the AE leading to death the outcome "fatal" should be selected. If the cause of death is unknown and cannot be ascertained at the time of reporting, "unexplained death" should be documented as event term.

8.3.7 Disease-related events/outcomes not qualifying as AEs or SAEs

Not applicable.

8.3.8 Adverse events of special interest

The following will be reported as AESIs:

- Myocarditis (all Levels of Certainty including 'Possible cases' (1 to 3) as per Brighton Collaboration Case Definition) 1 to 3 (Possible case), Myocarditis_Version_1.0_15 July 2021_FINAL_for Posting)
- Pericarditis (all Levels of Certainty including "Possible cases" (1 to 3) as per Brighton Collaboration Case Definition) 1 to 3 (Possible case), Pericarditis_Version_1.0_15 July 2021_FINAL_for Posting)
- Anaphylaxis
- Thromboembolic events (e.g., deep vein thrombosis, stroke, myocardial infarction)
- Immune thrombocytopenia
- Immune based neurologic events (e.g., optic neuropathy, Guillain-Barré syndrome)

8.4 Treatment of overdose

Any dose of trial treatment above the planned doses specified in this protocol will be considered an overdose. In the event of overdose:

- Closely monitor the trial subject for any AE/SAE and laboratory abnormalities (at least for 7 d).
- (At the discretion of the investigator) Give symptomatic treatment.

Clinical Trial Protocol BNT162-14 Page 53 of 91 Version: 4.0 Date: 20 JAN 2022

- Inform the sponsor's Medical Monitor as soon as possible; the sponsor's Medical Monitor should agree with the investigator regarding any action triggered, e.g., trial subject withdrawal from the trial or (if applicable) trial treatment.
- Document the quantity of the excess dose overdose in the CRF.

8.5 Treatments for specific adverse reactions

The adverse reactions determined for Comirnaty from the available unblinded clinical trial data (from BNT162-02/C4591001 [NCT04368728]) are mostly reflective of mild to moderate local and systemic reactogenicity events. The most frequent adverse reactions in trial subjects 16 yrs of age and older were injection site pain, fatigue, headache, myalgia and chills, arthralgia, pyrexia and injection site swelling, and were usually mild or moderate in intensity and resolved within a few days after vaccination. Additional adverse reactions determined from the clinical trial data are lymphadenopathy, nausea and malaise. Since authorization of Comirnaty, anaphylaxis has been reported and determined to be an adverse reaction. For details see the BNT162 IB.

Treatment of these adverse reactions is at the discretion of the investigators, however, the following suggestions are provided:

- After the first occurrence of flu-like symptomatology including fever, subjects can be treated with standard therapeutic dose of acetaminophen (preferable), or a nonsteroidal anti-inflammatory drug if acetaminophen is contraindicated.
- Corticosteroids should be avoided as either prophylaxis or treatment as it counteracts the effects of immunization.
- Ensure adequate hydration of trial subjects on the day of immunization. Consider administering fluids (e.g., water for drinking, 0.5 to 1.0 L) within ~2 h following the immunization per trial site standard.

If subjects experience enhanced respiratory disease symptom kinetics that are inconsistent with a relationship to RNA immunization, additional diagnostic measures should be considered, and the Medical Monitor should be informed.

If subjects report symptoms that could represent myocarditis or pericarditis, in addition to any medically indicated evaluations at the discretion of the investigators, the following United States Center for Disease Control (CDC) clinical recommendations for myocarditis and pericarditis following COVID-19 vaccination published on 28 May 2021 (https://www.cdc.gov/vaccines/covid-19/clinical-considerations/myocarditis.html) should be considered:

- For initial evaluation, consider an ECG, troponin level, and inflammatory markers such as C-reactive protein and erythrocyte sedimentation rate. In the setting of normal ECG, troponin, and inflammatory markers, myocarditis or pericarditis are unlikely.
- Consider consultation with:
 - Cardiology for assistance with cardiac evaluation and management.
 - Infectious disease and/or rheumatology to assist in this evaluation.

BioNTech SE
Confidential

Clinical Trial Protocol BNT162-14 Page 54 of 91 Version: 4.0 Date: 20 JAN 2022

• Where available, evaluate for potential etiologies of myocarditis and pericarditis, particularly acute COVID-19 infection (e.g., PCR testing), prior SARS-CoV-2 infection (e.g., detection of SARS-CoV-2 nucleocapsid-binding antibodies), and other viral etiologies (e.g., enterovirus PCR and comprehensive respiratory viral pathogen testing).

8.6 Safety stopping criteria

The SRC will review and evaluate the collected safety data for Group A and all reported SAEs from the trial at a minimum every 16 weeks during the trial and any emerging data concerns from Group B (e.g., SUSARs, Group B transplant data, etc.). A decision to stop treatment for an individual subject or to terminate the trial may be taken by the sponsor and investigator if safety concerns are identified by the SRC.

All SAEs will be reviewed by the SRC and all SUSARs as soon as possible. Any trial SAE but specifically a SUSAR in Group A may trigger a temporary stop of IMP administration to new subjects in Group A until the SRC has reviewed and discussed the relevant data and come to a recommendation to continue or permanently stop trial injections for Group A.

8.7 Pharmacokinetics

Not applicable.

8.8 Pharmacodynamics

Not applicable.

8.9 Genetics

After completion of the planned investigations of the immune response, residual blood and/or isolated PBMCs may be used for genetic analysis.

If not already done as part of the parent trial, blood and/or isolated PBMCs may be used for human leukocyte antigen (HLA) typing of a subject to allow additional analysis, e.g., characterization of T-cell receptor (TCR) repertoire and/or phenotypic characterization of antigen-specific T cells. Data generated with these additional analyses may provide information about the HLA dependency of immune response (e.g., if distinct HLA types have stronger/better immune response towards SARS-CoV-2).

Further, residual blood may also be used for profiling (e.g., by use of next generation sequencing) of B-cell receptor (BCR) and/or TCR variants in peripheral blood after vaccination.

Blood samples will only be used for genetic analysis if the trial subjects have provided separate informed consent for this genetic analysis.

8.10 Immune responses

Neutralizing antibody titers, antibody binding and CMI will be assessed at the times listed in the SoA (Section 1.3).

BioNTech SE
Confidential

Instructions on the sample collection, handling, and shipping will be provided in a Laboratory Manual. The methodology used for these assessments will be documented in the Biomarker Manual.

Leftover blood after completion of the serology assessments will be used for the analyses as described in Section 8.10.3 (i.e., for explorative biomarker/immunogenicity research purposes).

Trial subjects will be asked if leftover blood may also be used for research purposes, e.g., to develop methods, assays, etc., related to BNT162 vaccine candidates. The use of leftover blood for these purposes will require a separate informed consent.

8.10.1 Neutralizing antibody titers and antibody binding (NATAB)

Neutralizing antibody titers and antibody binding assessment comprise of:

- A functional antibody titer, e.g., VNT or an equivalent assay (e.g., pVNT assay).
 - Seronegative is defined as titers below the starting dilution (i.e., below the limit of detection of the assay).
- Seroconversion after immunization is defined as a 4-fold increase in titer.
 - o for seronegative pre-immunization sera: a titer ≥ 4-times the limit of detection.
 - for seropositive pre-immunization sera: a titer which is 4-fold higher than the measured pre-immunization titer.
- An antibody binding assay, e.g., ELISA or an equivalent assay.
 - Seroconversion after immunization is defined as a 4-fold increase in titer/antibody concentration.

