9.4.3 Secondary endpoints

The secondary endpoints are defined in Section 3.

All secondary immunogenicity analyses will be performed first with the IMM population (see Section 9.3) as this is an exploratory hypothesis-generating trial. However, the Immunogenicity Per Protocol set (IMMPP) population will also be analyzed.

The scheduled time points for assessment are given in the SoA (see Section 1.3).

The binary secondary endpoints will be summarized by group presenting absolute and relative frequencies (n and %) of subjects in each category for each assessment. The continuous secondary endpoints will be summarized by group using summary statistics.

For each subject and each time point, antibody titers will be defined based on the calculated geometric mean of antibody titers assessed in duplicate. Additionally, GMT with 95% CI will be presented.

Change in antibody titers to recombinant S1 and RBD protein derived from reference and B.1.351 strains will be assessed from baseline to time points as identified in the endpoints (see Section 3) and SoA (see Section 1.3). In addition to analysis of changes in

BioNTech SE	Clinical Trial Protocol	Page 59 of 91
Confidential	BNT162 14	Version: 4.0
Comidentia	DINT 102-14	Date: 20 JAN 2022

neutralizing antibody and binding antibody titers, functional cross-neutralization of vaccineinduced antibodies to B.1.351 in relationship to reference strain will be analyzed at time points identified in the secondary endpoints.

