6.1.3. Missing data

As a general rule, missing data will not be imputed (i.e., missing data will not be replaced but will be handled as "missing" in the statistical evaluation), with the following exceptions for summary analyses:

Clinical safety laboratory variables given as "<xx" will be evaluated as 0.5*xx in the summary tables. In the listings they will be displayed as "<xx" or similar.

Data values below lower limit of quantification (LLOQ) or detection (LLOD) will be imputed with 0.5*LLOQ or 0.5*LLOD, respectively, for the analysis of continuous data. Values above the upper limit of quantification (ULOQ) or detection (ULOD) will be imputed with 2*ULOQ or 2*ULOD, respectively, for the analysis of continuous data. In the listings they will be displayed as "<xx" or ">yy" as appropriate. In the tables they will be displayed as "<LLOQ"/("<LLOD" or ">ULOQ"/(">ULOD" in descriptive statistics (e.g., in mean, median, min, max) as appropriate. A footnote will be added to show the value of LLOQ or LLOD or ULOQ or ULOD.

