6.5.3. Seroconversion

Definition

Seroconversion is defined as a minimum of 4-fold rise of antibody titers as compared to

- parent trial (BNT162-01 or BNT162-04) baseline (only for titers derived from reference strain;baseline refers to pre-dose V1 in BNT162-01 or pre-dose V1 in BNT162-04)
- BNT162-14 baseline, i.e., the last value prior to first injection of IMP (Dose 1) given in this BNT162-14 trial on Day 1, including unscheduled visits (for both titers derived from reference strain and from SARS-CoV-2 variant B.1.351)

Analysis

The number of subjects with seroconversion in antibody titers (ELISA) derived from reference will be summarized by number and percentage with 95% confidence interval for all post-baseline time points for Group A, Group B and the immunology subset. The denominator of the percentages will be the number of subjects with data available at the respective visit.

The analysis based on BNT162-14 baseline, will be performed for antibody titers (ELISA) derived from SARS-CoV-2 variant B.1.351 for Group A only.

Seroconversion data of the antibody titer (ELISA) will be listed.

The same analysis will be repeated for neutralizing antibody titers

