6.5.4. SARS-CoV-2 functional cross-neutralization of variant B.1.351 to reference strain

Definition

The SARS-CoV-2 functional cross-neutralization of variant B.1.351 to reference strain is defined as the ratio of the GMT (reference / variant B.1.351). The geometric mean titer ratio is calculated as the GMT of reference divided by the GMT of variant B.1.351.

Analysis

For subjects of Group A, GMTs with 95% CI for all time points will be presented for variant B.1.351 and reference strain (see Section 6.5.1). Moreover, the GMT ratio between reference and variant will be presented.

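### Titers above the ULOQ are set to 2*ULOQ with no separate seroconversion rule, so a 4-fold rise on this trial's baseline can be misclassified, and GMT, GMFR and strain ratio are biased if many titers exceed the limit

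*Protocol*

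**What the plan says.** The imputation rule is in SAP 6.1.3: "Values above the upper limit of quantification (ULOQ) or detection (ULOD) will be imputed with 2*ULOQ or 2*ULOD, respectively". It is written for continuous data. Tables are to display such values as above the limit, and "A footnote will be added to show the value of LLOQ or LLOD or ULOQ or ULOD". No count or percentage of values above the limit is planned.

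SAP 6.1.2 and 6.5.2 define fold rise as the post-dose value divided by the baseline value. In SAP 6.5.3, "Seroconversion is defined as a minimum of 4-fold rise of antibody titers as compared to" either of two baselines: the parent-trial pre-dose value (reference strain only) or the BNT162-14 pre-dose value (reference strain and B.1.351). Protocol 8.10.1 words the seropositive case as "for seropositive pre-immunization sera: a titer which is 4-fold higher than the measured pre-immunization titer".

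SAP 6.1.1 computes GMT, GMFR and their t-based intervals from the logged results. For the strain comparison, SAP 6.5.4 states: "The geometric mean titer ratio is calculated as the GMT of reference divided by the GMT of variant B.1.351". The only sensitivity analysis for immunogenicity (SAP 6.6) excludes subjects infected during the trial. Neither document describes re-dilution or a censored-data method.

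**The concern.** A titer above the ULOQ says only that the true value exceeds the limit. Replacing it by one fixed number removes the post-dose information from the 4-fold decision and leaves it to the baseline alone. That matters most where the baseline may already be raised. Every subject was vaccinated in a parent trial, and Group A had two 30 µg doses. For B.1.351 the BNT162-14 baseline is the only one used.

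If many titers are affected, the same substitution biases GMT and GMFR. It also biases the reference/B.1.351 ratio, a secondary endpoint in the randomized group, when the two strains reach the limit at different rates. With no planned count above the ULOQ, a reader of the tables could not tell how far this applies.

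**Working it through.** The plan has no figure of its own to reproduce: no ULOQ, titer SD, share above the limit or sample size calculation is given. The classification result is exact. Everything else rests on stated assumptions.

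**1. Classification (exact).** Write U for the ULOQ and B for the baseline, and let the post-dose response be above U. Then computed fold = 2U/B, and 2U/B ≥ 4 if and only if B ≤ U/2. The true fold is only known to exceed U/B.

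| Baseline | Computed fold | Counted as 4-fold | True fold | Possible error |
|---|---|---|---|---|
| ≤ U/4 | ≥ 8 | always | > 4 | none |
| U/4 to U/2 | 4 to < 8 | always | more than 2 to 4, depending on B | false positive |
| U/2 to U | 2 to < 4 | never | more than 1 to 2, depending on B | false negative |
| > U (also imputed) | 1 | never | unknown | false negative |

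Examples: B = 0.5U with true titer 1.05U is a rise of 1.05/0.5 = 2.1, reported as 2/0.5 = 4.0. B = 0.6U with true titer 3U is a rise of 3/0.6 = 5, reported as 2/0.6 = 3.3.

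**2. GMT with half the titers above U (closed form).** For log10-normal titers with SD s centered at U, imputed GMT / true GMT = 10^(0.5·log10 2 − s/√(2π)) = 10^(0.1505 − 0.3989s). For s = 0.3, 0.4, 0.5 and 0.6 this is 1.07, 0.98, 0.89 and 0.81 to 0.82. The direction therefore depends on the SD.

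**3. GMT over a range (simulation, log10 SD 0.3 to 0.6; n = 60 is the larger Group A arm if 90 subjects are randomized 2:1).**

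| Share above U | Imputed/true GMT | Imputed/true SD of log titer | Coverage of nominal 95% CI |
|---|---|---|---|
| 10% | 1.00–1.04 | 1.00–1.09 | 94–95% |
| 30% | 0.95–1.08 | 0.91–1.10 | 88–95% |
| 50% | 0.82–1.07 | 0.78–1.00 | 73–95% |
| 70% | 0.61–0.99 | 0.59–0.80 | 0–95% |
| 90% | 0.30–0.75 | 0.32–0.46 | about 0% |

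**4. Response rate and GMFR (simulation).** Assumptions: log2 baseline SD 1.5, log2 rise SD 1.2, true GMFR 6, n = 30. The post-dose SD is √(1.5² + 1.2²) = 1.92 in log2, or 0.58 in log10. The true 4-fold rate is P(Z ≥ (2 − 2.585)/1.2) = 69%.

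| Share above U | 10% | 25% | 50% |
|---|---|---|---|
| Misclassified, of those above U | 4% | 11% | 25% |
| Misclassified, of all subjects | 0.4% | 2.7% | 12% |
| Reported 4-fold rate (true 69%) | 69% | 68% | 61% |
| GMT bias | +1% | −2.5% | −17% |
| GMT interval coverage | 95% | 95% | 89% |
| Imputed/true SD, log fold rise | 1.01 | 1.00 | 0.98 |

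At 50%, GMFR interval coverage is about 76%. Since the SD is almost unchanged, that loss comes from bias. With true GMFR 3, misclassification among those above U is about 17%, 26% and 34%; multiplied by the shares, this is about 1.7%, 6.5% and 17% of all subjects.

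A second set (log10 SD 0.4 for baseline and 0.35 for rise, true GMFR 8, true 4-fold rate about 80.5%) varies the baseline geometric mean:

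| Baseline geometric mean | Share above U | Counted 4-fold rate | Reported GMFR |
|---|---|---|---|
| U/16 | 29% | 79.9% | 7.83 |
| U/8 | 50% | 76.5% | 6.92 |
| U/4 | 72% | 64.7% | 5.18 |
| U/2 | 87% | 42.8% | 3.26 |

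**5. Strain ratio (simulation, log10 SD 0.4).** With 30%, 50%, 70%, 90% and 98% of reference titers above U, a true ratio of 2.0 is reported as 2.01, 1.91, 1.70, 1.35 and 1.12. A true ratio of 4.0 is reported as 4.09, 3.84, 3.27, 2.21 and 1.46.

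**The case against.** The strongest reply is that the rule covers continuous data only ("ULOQ) or detection (ULOD) will be imputed with 2*ULOQ or 2*ULOD, respectively, for the analysis of continuous data") while seroconversion is binary, so the SAP never says that the imputed value feeds the flag. That is fair: it is an inference. But seroconversion is defined from fold rise, fold rise is continuous, and no other rule is given. If the imputed value is not used, these subjects have no rule at all. GMT, GMFR and the ratio are affected on either reading.

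The second reply is that the premise is unproven. The assay methodology is in the Biomarker Manual, which is not part of these documents, and a wide range or re-dilution would remove the problem. This stands and limits what can be said about size. A reader might infer from third and fourth vaccinations that many titers must exceed the limit. The documents do not support that: some subjects had only one earlier injection, and transplant subjects are described as poor responders.

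Third, these are descriptive secondary endpoints without a hypothesis test, and tables flag values above the limit. Both are true, but the estimates and intervals are the immunogenicity result, and they still use the imputed value.

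Fourth, a censored model may be unstable in small cells, such as 15 transplant subjects or at most 15 HIV-positive subjects split by vaccine, and has no finite estimate when every value is censored. This stands, so the model belongs in a sensitivity analysis.

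**Conclusion.** The point holds. Against the BNT162-14 baseline, a post-dose titer above the ULOQ is classified by the baseline alone, and the result can be wrong whenever the baseline exceeds ULOQ/4. This needs no assay assumption beyond the natural reading of SAP 6.1.3 and 6.5.3 and a response imputed as a whole. The SAP does not say whether imputation is done per replicate or on the geometric mean of the two; if only one replicate exceeds the limit, the other also matters.

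The size is unknown. In the assumed scenarios the effect on the GMT and overall rates is small at 10 to 25% above the limit. From about half upward, GMT and GMFR are generally biased downward and the strain ratio moves toward 1 when reference titers are censored more often. With a log10 SD of 0.3, however, the GMT is still 7% too high at 50% and becomes clearly too low only beyond 70%. GMT coverage falls through bias and, at high shares, reduced variance. GMFR coverage falls mainly through bias.

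Three stronger readings are not supported:
- A reader might infer that GMFR intervals are too narrow because the imputed values are identical. The imputed fold still varies with the baseline, and its SD is nearly unchanged (ratios 1.01, 1.00, 0.98).
- A reader might infer that GMTs are always capped downward. At low shares the bias can be upward.
- A reader might infer that both seroconversion definitions fail. Against the parent-trial baseline, any subject at or below ULOQ/4 is classified correctly, and most are expected to be, since that sample precedes any trial vaccination.

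**What to change.** - In SAP 6.5.3, when the post-dose titer is above the ULOQ, count a 4-fold rise only if the baseline is at most ULOQ/4. Otherwise show the subject as not determinable, and give the rate with these subjects counted both as responders and as non-responders.
- In SAP 6.1.3, tabulate the number above the ULOQ by group, visit and strain, and state whether imputation is done per replicate or on the subject's geometric mean.
- Add a right-censored lognormal estimate of GMT, GMFR and the reference/B.1.351 ratio as a sensitivity analysis, for cells with enough uncensored values. Fix that minimum before the database snapshot. Treat GMFR as not estimable for subjects whose baseline also exceeds the ULOQ.

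The cost is SAP wording and limited programming, with no new data. The downside is that a response rate may be reported as a range when many titers exceed the limit. If none do, the results do not change.
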